APPENDIX VI ADVERSE EVENTS OF SPECIAL INTEREST (AESI)

System Organ Class	Event Term
Central Nervous system	Cerebral cortical atrophy
	Coma
	Demyelination
	Headaches
	Myelopathy
	Neuropsychological impairment (e.g.
	intellectual changes, dementia)
	Paralysis
	Symptomatic (e.g. neurological changes,
	seizures)
	White matter changes
	White matter necrosis
Cardiac/vascular	Angina
	Cardiac ischemia
	Cardiomyopathy
	Cor pulmonale
	Coronary artery disease
	Conduction abnormality
	Heart failure
	Hypertension
	Increased capillary permeability
	Myocarditis
	Neovascular formation
	Pericardial effusion
	Pericarditis
	Valvular heart disease
	Vascular congestion
	Vascular endothelial changes (e.g. subintimal
	fibrosis, lumen narrowing, etc)
	Vascular obstruction (e.g. pulmonary capillary
	obstruction, intracranial vascuopathy, etc)
Endocrine toxicity	Calcitonin deficiency
	Delay or failure to complete puberty
	Growth hormone deficiency
	Hypothalamic pituitary axis dysfunction
	Increased obesity (children)
	Increased prolactinemia
	Precocious puberty
	Premature menopause
	Thyroid abnormalities (hypothyroid,

	thyroiditis, etc)
Even and Form	Blindness
Eyes and Ears	Cataracts
	Glaucoma
	Hearing loss Panophthalmitis
	*
	Retinopathy
Gastrointestinal	Abdominal pain
Gastronnestinai	Bowel perforation
	Bowel obstruction
	Chronic atrophic gastritis
	Chronic diarrhea
	Dyspepsia
	Dysphagia Malabsorption
	Proctitis
	Rectal bleeding Rectal or anal stricture
	Separation of bowel loops (fibrosis, strictures
	and narrowing)
	Ulcers (e.g. peptic, duodenal, etc)
	Olcers (e.g. peptic, duodenai, etc)
Genitourinary	Albuminuria
	Altered growth of reproductive organs
	Bladder contracture
	Cystitis
	Diminished erectile potency
	Elevated creatinine
	Elevated urea
	Hematuria
	Hypertension
	Impotency
	Renal dysfunction
	Renal failure
	Trigonal ulcer
	Urethral stricture
Head and Neck	Arytenoid edema
	Chondritis
	Fibrosis/atrophy in muscles
	Tracheal aspiration
	Voice change
	Xerostomia (permanent)
Hepatic	Abnormal liver functions tests
	Ascites
	Hepatic insufficiency
	Troputo insufficiency

Malignancies	Bone sarcomas
	Esophageal cancer
	Leukemias
	Mesothelioma
	Myelodysplastic syndrome
	Skin cancer
	Thyroid cancer
	Other cancers
Peripheral nervous system	Numbness
× ×	Peripheral nerve deficits
	Shock like paresthesias
Pulmonary	Bronchiolitis
	Pleural fibrosis
	Pneumonitis
	Pneumothorax
	Pulmonary failure
	Pulmonary fibrosis
	Respiratory insufficiency
Skin	Skin lesions
	Skin necrosis
Soft Tissue and bone	Atrophy
	Bone pain or tenderness
	Bone sclerosis
	Contracture
	Fibrosis or induration
	Impaired growth
	Joint stiffness
	Loss of subcutaneous tissue
	Secondary fractures

Ultratrace Iobenguane I 131 Protocol No. MIP-IB12B	1	APPENDIX V	/II: SCHEDI	DIX VII: SCHEDULE OF PROCEDURES	CEDURES			Pheochro Page 96	Pheochromocytoma Page 96
	Screening/ Baseline	Imaging Dose/ Scans	Therapeutic Doses	Ultratrace I 131 Scan	Post Therapy I	Post Each Therapy	Post Therapy I	y I	Long Term Follow Up* Every 6 mo
Procedure/Test	Week -4 to Imaging Dose	Imaging Dose within 30 days of therapeutic dose	Day 0 and Month 3	Within 7 days after each therapeutic dose	Weekly through 24 Weeks	6 weeks after each therapy	Monthly post 1 st Therapy	3, 6, 9 ,12 Months post 1st Therapy	Years 2 through 5 after 1st Therapy
Medical History	X								
Physical Exam/Month 12 Dry Mouth ¹	Х	X	X			X (±10 days)		Х	
Weight	Х	X	X						
Karnofsky Performance	X		X			X (±10 days)		X	
Vital Signs ²	Х	Х	Х						
Blood Pressure & Heart Rate by professional staff ²	X			X	1 x a week (at weeks when not collected twice weekly through Week 24)	2X a week in the first six weeks after each dose	1x month (Months 7-12)		
Patient Self-taken Blood Pressure	Subjects will	Subjects will measure their blood pressure at least 1-2 times per week (preferably no more than 7 days between measurements) at the same time of day from the Screening/Baseline period through Month 12.	pressure at least 1 ie time of day fron	-2 times per week n the Screening/Ba	(preferably no mor seline period throu	e than 7 days b gh Month 12.	etween measu	rements) at	
Antihypertensive Status & Meds	Use of ant	Use of antihypertensive medication will be measured through standard, ongoing reporting of concomitant medications throughout the study	ation will be meas	sured through stand	lard, ongoing repoi	ting of concom	litant medicati	ons throughor	at the study
Adverse Events ⁴	AEs collecte	AEs collected until last day of Week 15 after last dose/CM throughout the study until completion of follow-up/ AEs of Special Interest after 16 weeks after the last therapeutic dose until completion of follow-up	/eek 15 after last weeks after	5 after last dose/CM throughout the study until completion of followeeks after the last therapeutic dose until completion of follow-up	ut the study until c c dose until comple	ompletion of fo tion of follow-1	ollow-up/ AEs up	of Special Int	cerest after 16
Concomitant Medications			Concomitant	Concomitant medications taken throughout the study will be recorded	throughout the stu	dy will be recor	ded		
Hematology, Chem, UA ⁵	Х	Х	Х		Week 2-Week 24	Х	1x month (Months 7-12)		
TSH, T3, T4	Х							X (Month 12 ONLY)	

MIP-IB12B_CSP_V1a3_21Mar2014 CONFIDENTIAL

Ultratrace Iobenguane I 131 Protocol No. MIP-IB12B	31	APPENDIX	VII: SCHED	DIX VII: SCHEDULE OF PROCEDURES	DCEDURES			Pheochro Page 97	Pheochromocytoma Page 97
	Screening/ Baseline	Imaging Dose/ Scans	Therapeutic Doses	Ultratrace I 131 Scan	Post Therapy I	Post Each Therapy	Post Therapy I	y I	Long Term Follow Up* Every 6 mo
Procedure/Test	Week -4 to Imaging Dose	Imaging Dose within 30 days of therapeutic dose	Day 0 and Month 3*	Within 7 days after each therapeutic dose	Weekly through 24 Weeks	6 weeks after each therapy	Monthly post 1 st Therapy	3, 6, 9 ,12 Months post 1st Therapy	Years 2 through 5 after 1st Therapy
Renal function (GFR or 24 hr $CC)^6$	Х							Month 6 & 12	
Renal Volume	Х								
Tumor Markers	X				Every 2 weeks during weeks 2-24		1x month (Months 7-12)		X
Pregnancy Test, serum or urine(if applicable)	X (serum)	X (urine, within 48hrs prior to dose)	X (urine, within 48 prior to dose)						
CT or MR Scan of chest, pelvis and abdomen ^{7}	Х							X	Х
Optional FDG scan	Х							Х	
Bone Scan ⁸	X							X^8	
ECG ⁹		Х		Х					
Holter Monitor (24 hours) ¹⁰			Х						
SSKI Administration ¹¹		X (Day -2 to Day 0)	Х						
Imaging Dose 3 to 6 mCi Ultratrace I 131		Х							
Imaging Scans Ultratrace I 131 ¹² (scintigraphic)		X (3)		Х					
Dosimetry Calculation for Therapy Dose		X (Day -2 to Day 0)							
Therapeutic Dose Ultratrace I 131			X(dose 1 on day 0 and dose 2 on Month 3)						
EORTC QLQ-C30 ^{13/} NIH Pheo Clinical Questionnaire ¹³	X (2)				Week 3,6,10,12,15, 18,22		Monthly Months 6- 12		

MIP-IB12B_CSP_V1a3_21Mar2014 CONFIDENTIAL

MIP-IB12B_CSP_V1a3_21Mar2014 CONFIDENTIAL

I 131	2B
enguane]	MIP-IB12B
obeng	, ,
	l No.
tratrace]	rotocol
Π	Ě

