10 countries. They found a total of 116 evaluable patients. A majority of the patients were selected for treatment based upon positive tracer uptake studies. The cumulative dose of carrieradded iobenguane I 131 administered ranged from 96 to 2,322 mCi, with a mean (\pm SD) of 490 + 350 mCi. The patients received a mean single therapy dose of 158 mCi and the number of doses administered ranged from 1 to 11, with a mean (\pm SD) of 3.3 + 2.2 doses. Initial symptomatic improvement was achieved in 76% of patients, tumor responses in 30%, and hormonal responses in 45%. Five patients had complete tumor and hormonal responses, ranging from 16 to 58 months, which were sustained at the time of reporting. Patients with metastases to soft tissue had more favorable responses to treatment than those with metastases to bone. No difference was noted in the age between the responders and non-responders. Adverse effects, recorded in 41% of the treated patients, were generally mild except for one fatality from bone marrow aplasia. Among 89 patients with follow-up data, 45% of the responders had relapsed with recurrent or progressive disease after a mean interval of 29.3 + 31.1 months (median 19 months). Of patients with an initial response to carrier-added iobenguane I 131, death was reported in 33% after a mean (\pm SD) of 23.2 + 8.1 months (median 22 months) following treatment. Of non-responders, death was reported in 45% after a mean (\pm SD) of 14.3 + 8.3 months (median 13 months). The reviewers concluded that carrier-added iobenguane I 131 therapy may be a useful adjunct in selected patients with malignant pheochromocytoma or paraganglioma.

Mukherjee et al.¹⁵ reported carrier-added iobenguane I 131 treatment of 15 patients with metastatic pheochromocytoma or paraganglioma. The patients were treated repeatedly to a cumulative dose of 592 mCi; this ranged from 200 to 1,592 mCi. No patients had complete remissions, but 82% had stable disease. The overall 5-year survival was 85%. Hormonal control was attained in 53%.

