study provided adequate safety and efficacy data to demonstrate a positive benefit for treatment of malignant pheochromocytoma/paraganglioma, and an acceptable safety profile. These patients received the highest dosage of Ultratrace iobenguane I 131 that did not exceed the protocol-mandated maximum radioactivity dosage of 450, 525, 600, or 675 mCi for patients at the planned 6, 7, 8, or 9 mCi/kg dose increments, respectively. The best response to treatment (partial response [PR] in 19% of patients) was observed for patients who received >500 mCi. The maximum dose level investigated was 9 mCi/kg, at which 2 patients experienced DLTs. The MTD was defined as the dose immediately below the level at which escalation was stopped due to the occurrence of \geq 2 DLT's in a dose cohort, therefore, the MTD was determined to be 8 mCi/kg. Two other subjects also experienced hematological DLTs, one in the 7 mCi/kg dose cohort and one in the 8 mCi/kg dose cohort.

All 21 patients who received Ultratrace iobenguane I 131 had at least 1 treatment-related TEAE, for a total of 454 TEAEs reported. The majority of TEAEs (68.9%) were considered related to the administration of Ultratrace iobenguane I 131. Adverse events assessed as severe or life-threatening in severity were reported in 16 (76.2%) patients and were consistent with the anticipated hematologic consequences of bone marrow suppression (pancytopenia, thrombocytopenia, leukopenia, and neutropenia). A total of 15 (71%) of the 21 patients experienced 34 SAEs during the study. The majority of SAEs were not considered related to the administration of Ultratrace iobenguane I 131; SAEs of pancytopenia and dehydration (both SAEs occurred in 2 patients each), platelet count decreased (2 SAEs in 1 patient), and the single SAEs of febrile neutropenia, leukopenia, neutrophil count decreased, neutropenia, and white blood cell count decreased were considered related to study drug administration. There were 5 treatment-emergent deaths reported as AEs (hepatic failure, spinal disorder, thalamic infarction, pulmonary embolism, and metastasis). All deaths occurred from approximately 2.5 months to up to 22 months after the imaging dose and all were assessed as unrelated to study treatment.

7.6.3 Study MIP-IB13: A Phase 2a Study of Ultratrace[®] Iobenguane I 131 in Patients with Relapsed/Refractory High Risk Neuroblastoma

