12. REPORTING SAFETY INFORMATION

The site staff will screen subjects for adverse events during scheduled visits, non-scheduled visits or safety call at 16 weeks after the last therapeutic dose (see Section 11.5.2). Any untoward medical event that is discovered from the time of signed informed consent until the last day of week 15 from the last infusion of therapeutic administered Ultratrace iobenguane I 131 will be collected and reported as an adverse event. Thereafter, adverse events of special interest (AESI), will be collected starting 16 weeks after the last therapeutic administration of Ultratrace iobenguane I 131 until completion of the follow up period.

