12.1.2.1 Reporting Adverse Events of Special Interest

Definition:

An **adverse event of special interest (AESI)** is a serious or nonserious event of scientific and medical concern specific to Ultratrace iobenguane I 131. The event may require further investigation, and depending on the nature of the event, submission to the FDA, Health Canada and other applicable regulatory authorities. For the purposes of this trial AESI have been predefined by MIP (See Appendix IV) to identify any signs of late stage radiation toxicity in the study population. Additionally, if an investigator determines an event, not listed within the appendix, is medically significant and may be causally related to the study product, the event will be reported to MIP's designee (see Appendix VIII), expeditiously, for real-time monitoring. Adverse events of special interest would only be classified as SAEs if the Investigator determined that they met established regulatory criteria as outlined above for serious events or, if upon further review by the sponsor, the events meet SAE criteria.

All adverse events of special interest will be reported starting 16 weeks after the last therapeutic dose until completion of the follow-up period, on a Serious Adverse Event Report (SAER) form and must be completed by the Investigator or designee and telephoned, emailed or faxed to MIP's designee within 24 hours after the Investigator first becomes aware of the adverse event (see Appendix VIII). A separate SAER will be needed for each reported AE of interest so that the onset, resolution date, outcome and causality can be assessed for each event. Any source documents relevant to the event should be forwarded to MIP's designee with the SAER form. The SAER form must be signed and dated by the Investigator. The Original copy must remain on site with the CRF.

A new follow-up SAER will be completed by the Investigator if important follow-up information (i.e., diagnosis, outcome, causality assessment, results of specific investigations) are made available after submission of the initial form. The follow up SAER form must be signed and dated by the Investigator. The follow-up form and any additional source documentation regarding the event will be sent to MIP, or designee, as described above.

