7.5.5. Hematologic Adverse Events

AEs of a hematologic nature are of particular interest in this study. However, similar hematologic AEs are often coded under different preferred terms (e.g., ‘leukopenia’ and ‘white blood cell count decreased’). An additional summary of hematologic events categorized as either grade 3, grade 4, or as SAEs, combining such similar preferred terms, will be presented. The following preferred terms are classified as hematologic AEs. This list may be updated prior to database lock and analysis if additional preferred terms are reported.

- ‘Anaemia’
- ‘Anaemia macrocytic’
- ‘Febrile neutropenia’
- ‘Haemolytic anaemia’
- ‘Haematocrit decreased’
- ‘Haemoglobin decreased’
- ‘International Normalised Ratio Increased’
- ‘Leukopenia’
- ‘Leukocytosis’
- ‘Lymphopenia’
- ‘Lymphocyte count decreased’
- ‘Lymphocyte percentage decreased’
- ‘Monocyte count decreased’
- ‘Monocyte count increased’
- ‘Eosinophil count decreased’
- ‘Neutropenia’
- ‘Neutrophil count increased’
- ‘Neutrophil percentage increased’
- ‘Pancytopenia’
- ‘Red blood cell count decreased’
- ‘Thrombocytopenia’
- ‘Platelet count decreased’
- ‘Platelet count increased’
- ‘Mean platelet volume decreased’
- ‘Neutrophil count decreased’

- ‘Neutrophil percentage decreased’
- ‘White blood cell count decreased’
- ‘Prothrombin time prolonged’

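### Neither AESI list has a blood or bone-marrow row, so a new late non-fatal marrow event short of MDS or leukemia is reportable only on the investigator's judgment, mainly in Years 2-5

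*Protocol*

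**What the plan says.** **Collection.** Protocol Section 12 collects all adverse events up to the last day of Week 15 after the last therapeutic infusion. It continues: "Thereafter, adverse events of special interest (AESI), will be collected starting 16 weeks after the last therapeutic administration", to the end of follow-up. Section 12.1.2 ends SAE reporting at the same point, except that deaths are reported throughout, whatever their cause.

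**The lists.** The protocol names the AESIs in the table headed "APPENDIX VI ADVERSE EVENTS OF SPECIAL INTEREST (AESI". Its blood-related terms are leukemias and "Myelodysplastic syndrome", both under malignancies. SAP Appendix 2 revises the list and also has only those two.

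**Unlisted events.** Section 12.1.2.1 adds a route "if an investigator determines an event, not listed within the appendix, is medically significant and may be causally related to the study product". Section 12.1.2 adds another for serious occurrences outside the window that are believed to be related.

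**What the plan says about marrow.** On the earlier dose-escalation study, Protocol Section 7.6.2 reports two patients with dose-limiting toxicities at 9 mCi/kg and then: "Two other subjects also experienced hematological DLTs, one in the 7 mCi/kg dose cohort and one in the 8 mCi/kg dose cohort". Severe or life-threatening events occurred in 16 of 21 patients and were described as in keeping with marrow suppression. The review of 116 patients given carrier-added drug (Section 7.2) calls adverse effects "generally mild except for one fatality from bone marrow aplasia". SAP Section 7.5.5 states: "AEs of a hematologic nature are of particular interest in this study".

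**The concern.** Section 12.1.2.1 gives the purpose of the AESI list as finding signs of late radiation toxicity, and from Week 16 the list decides what sites must report. A list that covers 13 organ classes but omits the organ that produced dose-limiting toxicities leaves late non-fatal marrow events to individual attribution.

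That attribution is hardest in subjects with marrow metastases or later anticancer therapy. Progression and new anticancer therapy are both reasons for discontinuation (Section 9.7). Subjects who discontinue during long-term follow-up are followed only for AESIs, possibly by telephone (Section 9.8). At stake is whether the late-safety tables can describe marrow outcome beyond the first year. The primary endpoint and the success criterion are not affected.

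**Working it through.** The plan states no figure to reproduce. The check compares the lists, the collection rules, the time line and the planned outputs.

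**1. Lists, term by term.** Protocol Appendix VI covers central nervous system, cardiac/vascular, endocrine, eyes and ears, gastrointestinal, genitourinary, head and neck, hepatic, malignancies, peripheral nervous system, pulmonary, skin, and soft tissue and bone. None of the 13 includes cytopenia, pancytopenia, aplasia or marrow failure. SAP Appendix 2 adds terms such as alopecia and oligospermia but none for marrow.

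**2. What is captured from Week 16 without a relatedness judgment.**
- Deaths (Section 12.1.2).
- MDS and leukemia, as listed AESIs.
- Adverse events that began earlier, which are followed toward resolution (Section 12.1.5).
- Laboratory counts: weekly for at least 12 weeks after dose 2, then monthly in Months 7-12 (Section 11.5.4).

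What remains is a new, non-fatal cytopenia or marrow failure that is not MDS or leukemia. Up to Month 12 the counts would show it. After that, Section 11.5.4 lists no time point, and the Schedule of Procedures has no hematology entry in the Years 2-5 column.

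**3. Time line, in weeks from the first therapeutic dose.** Month 12 = 365/7 = 52.1. Year 5 = 5 × 365.25/7 = 260.9. Weeks without scheduled counts = 260.9 − 52.1 = 208.8. With the last dose at week L, the AESI-only period starts at L + 16. Section 10.2 limits a delayed second dose to Week 24.

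| Case | L | Start (L + 16) | Weeks with counts (52.1 − start) | Weeks to Year 5 (260.9 − start) | Share without counts |
|---|---|---|---|---|---|
| One dose | 0 | 16 | 36.1 | 244.9 | 208.8/244.9 = 85.2% |
| Dose 2 at Week 12 | 12 | 28 | 24.1 | 232.9 | 208.8/232.9 = 89.6% |
| Dose 2 at Week 24 | 24 | 40 | 12.1 | 220.9 | 208.8/220.9 = 94.5% |

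Starting one week earlier, at the close of Week 15, gives 208.8/245.9 = 84.9%, 208.8/233.9 = 89.3% and 208.8/221.9 = 94.1%. The choice moves each share by less than half a percentage point.

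**4. Where a late, serious, unlisted marrow event would appear if a site reports it.**
- SAP 7.5.1 limits the adverse-event tables to treatment-emergent events, which end 15 weeks after the last dose. It states no exception for the hematologic summary in 7.5.5.
- The separate table in 7.5.1 for events from Week 16 leaves out SAEs and AESIs.
- The SAE table in 7.5.4 counts treatment-emergent SAEs. Later ones go to listings.
- The AESI summary in 7.5.8 takes the events of special interest indicated in Protocol Section 12.1.2.1. The SAP does not say whether an unlisted event reported by the judgment route counts as one, and Appendix 2 has no term for it.

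Unless it is classed as an AESI, the event therefore appears only in listings.

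**The case against.** Much of the opposing case stands.

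- **Counts to Month 12 are displayed well.** SAP 7.5.9 plans values by visit window, grade 3/4 counts, listings of nadir and time to recovery to grade 1 or less for four hematologic parameters, and by-subject figures for neutrophils and platelets. A reader might infer that the acute nadir hides a persistent cytopenia, because it sets the worst grade in the shift tables. These other outputs contradict that.
- **The judgment route has a low bar.** Section 12.1.4 treats an event as related when causality cannot definitively be ruled out. A reader might infer that a late cytopenia blamed on the disease is never recorded. On that definition it is lost only if the investigator is definite, and non-serious unlisted events that sites do report get their own table.
- **The evidence is mostly acute.** Section 7.3 reports counts back to pre-treatment values by 8 weeks with this product. The dose-limiting toxicities carry no information on late onset. The aplasia death was with carrier-added drug and has no stated timing, and a death would be reported here anyway. A reader might infer that non-MDS marrow failure is the late harm most to be expected; the documents do not support that ranking.

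SAP 7.5.8 also says the AESI list will be updated before database lock if further terms are reported. That does not close the gap, because it changes the analysis and not what sites must send.

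**Conclusion.** The point holds in a limited form. From Week 16 after the last therapeutic dose, reporting of a new non-fatal cytopenia or marrow failure that is not MDS or leukemia rests on the investigator's judgment, because neither AESI list has a blood or marrow row. It would be wrong to say that such events are collected in no other way, since scheduled counts continue for 12 to 36 weeks of that period. The gap lies mainly in the last four years, which are 85% to 95% of it. The SAP also has no clear summary table for a late serious event of this kind.

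The shares assume follow-up to Year 5 and a second dose, where given, between Weeks 12 and 24. They measure time without scheduled counts, not events missed; that number cannot be derived from the documents. This is a worthwhile, inexpensive improvement to late-safety capture and not a threat to the efficacy conclusion.

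**What to change.** Add a blood and bone-marrow row to Protocol Appendix VI and SAP Appendix 2, with these terms: bone marrow failure or aplasia; pancytopenia; grade 3 or higher cytopenia persisting or newly occurring beyond 16 weeks after the last dose; and transfusion dependence. Known events are then reported and tabulated whatever the attributed cause.

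Two consequential edits are needed. SAP 7.5.8 summarizes AESIs by onset beyond 16 weeks, so it needs a line saying how a cytopenia that began earlier and persists is counted. Protocol Section 12.1.2.1 points to Appendix IV (the questionnaires) for the AESI list and should point to Appendix VI.

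The cost is one row in two appendices and a modest number of extra AESI reports. Some will be disease-related, and the causality assessment already required on each report separates them. Two limits remain. With no new tests, cytopenias in Years 2-5 are still found only through routine care. Enrollment closed in December 2015 (SAP 4.1), so new site reporting helps only subjects still in follow-up, while the tabulation change can apply to every event already reported.
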